### 10.2.3. Assessment of ability to perform usual daily activities

If possible, subjects/caregivers will be asked to provide a daily assessment of the subject's ability to perform usual daily activities using a 0 to 10 visual analogue scale, where 0 = Unable to perform usual activities at all, and 10 = Able to perform usual activities fully. The subject will also assess his/her time lost from work, if applicable. The subject/care giver will be asked to record these assessments in the subject diary once daily from Baseline through Day 13 and prior to the subject's clinic visit on Day 14.

### 10.2.4. Influenza-Related Complications

Study personnel will evaluate the subject at Screening and Days 3, 7, and 14 for the presence of clinical signs and/or symptoms of the following IRC:

- Sinusitis
- Otitis media
- Bronchitis
- Pneumonia

**Note that subjects with clinical signs and/or symptoms consistent with bacterial infections, including: otitis media, bronchitis, sinusitis, and/or pneumonia at screening are not eligible for enrollment in this study (see exclusion criteria in Section 8.2).**

If an IRC is suspected, then a targeted physical examination will be conducted to confirm the presence or absence of the IRC. If the Investigator determines that the subject experiences (or is presumed to

experience) an IRC as noted above, he/she will record that assessment and any medication used to treat the condition in the source record and record the IRC and medications in the case report form (CRF). The Investigator will promptly provide appropriate treatment for any suspected or proven IRC. Such information describing IRC signs and/or symptoms should not be reported as AEs. Any reactions at the site of the IV drug administration will be recorded as an AE.

#### **10.2.5. Hospital Admission**

In the event that a subject requires admission to a hospital at any time during the study additional information on the hospital admission will be collected. See Section 11.1.5 for serious adverse event (SAE) reporting details.

#### **10.3. Virology Samples**

Bilateral mid-nasal swab specimens will be collected for virologic analysis. Samples will be collected at Baseline, Day 3, Day 7, and Day 14.

Virology laboratory tests will include viral sub type characterization from the baseline sample, laboratory culture and analysis by  $\log_{10}$  TCID50, RT-PCR assay, viral susceptibility to peramivir, oseltamivir, and zanamivir, and genotypic analysis of primary virus isolates.

## 11. ASSESSMENT OF SAFETY

Safety will be evaluated through assessments of AEs, pregnancy outcomes, laboratory analyses (clinical chemistry, hematology, and urinalysis), vital signs, and physical examinations.

### Adverse Events

Adverse events will be assessed and recorded at the indicated time points (see schedule of assessments, [Table 1](#)). AEs will be recorded on Screening, Day 1, Day 3, Day 7 and Day 14/Early Withdraw visits. Adverse events will be graded through use of the Division of Acquired Immune Deficiency Syndrome (DAIDS) Tables for Grading Adult and Pediatric Adverse Experiences (see [Appendix 16.2](#)). Any Grade 3 and Grade 4 clinical AEs or laboratory abnormalities that are judged to be possibly, probably, or definitely related to study treatment will be promptly (within 72 hours) reported to the study medical monitor unless the event meets criteria for an SAE, in which case they must be reported within 24 hours. Influenza-related complications are not considered AEs unless they meet the criteria for SAEs. Full details on recording and reporting AEs are provided in [Section 11.1.2](#).

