### 8.1. Subject Inclusion Criteria

1. Male and female subjects age  $\geq$  18 years.
2. The subject must meet one of the following two criteria:
  - a. A positive influenza Rapid Antigen Test (RAT) and/or a FDA-approved PCR test and at least one clinical sign or symptom consistent with acute influenza infection as listed in 2b below.

**OR**

- b. Clinical signs and symptoms consistent with acute influenza infection consisting of an oral temperature  $\geq$  100°F (37.8°C) with at least one respiratory symptom of at least moderate severity (cough or rhinitis) and at least one constitutional symptom of at least moderate severity (myalgia [aches and pains], headache, feverishness, or fatigue). **Note: Enrollment at each site by clinical symptoms alone will be approved by the Sponsor at the beginning of each influenza season once influenza has been confirmed in the local community. The Sponsor may withdraw approval for symptomatic screening in any season based upon trends in influenza surveillance data. Prior to Sponsor approval or after approval is withdrawn, Criteria 2 must be met by a positive influenza RAT test and/or PCR. During the period of approval, clinical symptoms alone will be adequate to meet Criteria 2.**
3. Onset of symptoms no more than 48 hours before presentation for screening. However, due to historically delayed presentation for medical care in the adult population, approximately 20% of the elderly population may be enrolled with symptoms starting  $>$  48-hours but  $\leq$  72-hours prior to presentation for screening. Note: Time of onset of illness is defined as either (1) the time when the temperature (either oral or rectal) was first measured as elevated (at least one °C of elevated temperature), OR (2) the time when the subject experienced the presence of at least one respiratory symptom AND the presence of at least one constitutional symptom together.
4. Either age  $\geq$  65 years AND/ OR presence of one of the following risk factors:
  - a. Pregnancy, including women who are up to 2 weeks postpartum
  - b. Resident of a nursing home or long-term care facility
  - c. History of chronic lung disease including obstructive pulmonary disease (COPD), persistent asthma or cystic fibrosis
  - d. History of heart disease including myocardial infarction, angina requiring treatment, congestive heart failure requiring treatment, arrhythmia including atrial fibrillation and valvular dysfunction

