4.2. INTENT-TO-TREAT INFECTED POPULATION

The ITTI population will include all subjects who are enrolled, treated, and have influenza type A or B confirmed by PCR. The ITTI population will be used for analyses of effectiveness.

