5.4. PROTOCOL DEVIATIONS

Any deviation from protocol will be listed by subject and date. The type of deviation along with a description and any additional comments about the deviation will be listed.

In cases where the statistical analysis plan differs from the protocol, the statistical analysis plan will supersede the protocol.

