Figure 14.2.3.4	Median (with IQR) Change from Baseline Viral Titers (TCID ₅₀ /mL) by Study Visit: Subjects with Positive Baseline Titers: Intent-to-Treat Infected Population
Table 14.2.4.1	Summary of Viral Shedding by Study Visit; Subjects with Positive Baseline Titers: Intent-to-Treat Infected Population
Table 14.2.4.1.X	Summary of Viral Shedding by Study Visit: Subjects with Positive Baseline Titers: Viral Subtype: Intent-to-Treat Infected Population
Table 14.2.5.1	Summary of RT-PCR Result by Study Visit: Subjects with Positive Baseline RT-PCR: Intent-to-Treat Infected Population
Table 14.2.5.1.X	Summary of RT-PCR Result by Study Visit: Subjects with Positive Baseline RT-PCR: Viral Subtype: Intent-to-Treat Infected Population

Output Number	Output Title
Table 14.2.6	Change of Influenza Virus Susceptibility to Neuraminidase Inhibitors: Intent-to-Treat Infected Population
Table 14.2.7	Summary of Influenza-Related Complications and Hospitalizations: Intent-to-Treat Infected Population
Table 14.2.8	Number of Doses of Antipyretic Medications: Intent-to-Treat Infected Population
Table 14.2.9.1	Summary of Subject-Rated Assessment of Ability to Perform Daily Activities: Intent-to-Treat Infected Population
Table 14.2.9.2	Time to Return to Usual Activities: Intent-to-Treat Infected Population
Table 14.3.1.1	Overall Summary of Treatment-Emergent Adverse Events: Safety Population
Table 14.3.1.2	Treatment-Emergent Adverse Events by System Organ Classification, Preferred Term and Greatest Severity: Safety Population
Table 14.3.1.3	Treatment-Emergent Adverse Events by System Organ Classification and Preferred Term: Safety Population
Table 14.3.1.4	Treatment-Emergent Adverse Events Possibly, Probably, or Definitely Related to Study Drug by System Organ Classification and Preferred Term: Safety Population
Table 14.3.1.5	Treatment-Emergent Serious Adverse Events by System Organ Classification and Preferred Term: Safety Population
Table 14.3.1.6	Treatment-Emergent Adverse Events Leading to the Discontinuation of Study by System Organ Classification and Preferred Term: Safety Population
Table 14.3.1.7	Treatment-Emergent Adverse Events Leading to the Discontinuation of Study Drug by System Organ Classification and Preferred Term: Safety Population
Table 14.3.1.8	Treatment-Emergent Adverse Events Occurring in $\geq 10\%$ of Subjects by Preferred Term: Safety Population

Output Number	Output Title

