Table 14.3.4.1.1	Summary of Chemistry Laboratory Values by Study Visit: Safety Population
Table 14.3.4.1.2	Summary of Hematology Laboratory Values by Study Visit: Safety Population
Table 14.3.4.2	Graded Laboratory Toxicities: Safety Population
Table 14.3.4.3.1	Laboratory Shifts from Baseline to Day 7 - Chemistry: Safety Population
Table 14.3.4.3.2	Laboratory Shifts from Baseline to Day 7 - Hematology: Safety Population
Table 14.3.4.3.3	Laboratory Shifts from Baseline to Day 7 - Urinalysis: Safety Population
Table 14.3.5	Study Drug Exposure: Safety Population
Table 14.3.6	Summary of Vital Signs by Study Visit: Safety Population
Table 14.3.7.1	Concomitant Medications by Generic Name and Drug Classification: Safety Population
Table 14.3.7.2	Antipyretic Concomitant Medications by Generic Name and Drug Classification: Safety Population
Table 14.3.7.3	Concomitant Medications Used to Treat Influenza Symptoms by Generic Name and Drug Classification: Safety Population
Table 14.4.1.1	Summary of Plasma Concentrations of Peramivir by Time Point: Intent-to-Treat Population
Table 14.4.1.2	Summary of Plasma Concentrations of Peramivir by Time Point: Exposure-Response Population
Figure 14.4.2	Relationship between Time to Alleviation of Influenza Symptoms and Peramivir Plasma Concentrations at 30-60 Minutes Post-Dose: Exposure-Response Population

Output Number	Output Title
Figure 14.4.3	Relationship between Viral Change from Baseline and Peramivir Plasma Concentrations at 30-60 Minutes Post-Dose: Exposure-Response Population
Listing 16.2.1	Study Completion: Intent-to-Treat Population
Listing 16.2.2	Protocol Deviations: Intent-to-Treat Population
Listing 16.2.4.1	Inclusion/Exclusion Criteria: Intent-to-Treat Population
Listing 16.2.4.2	Subject Eligibility: Intent-to-Treat Population
Listing 16.2.4.3	Demographics: Intent-to-Treat Population
Listing 16.2.4.4	Medical History: Intent-to-Treat Population
Listing 16.2.4.5	Prior and Concomitant Medications: Intent-to-Treat Population
Listing 16.2.5.1	Study Medication Administration: Intent-to-Treat Population
Listing 16.2.5.2	Pharmacokinetic Sample Collection Time and Concentrations: PK Population
Listing 16.2.6.1.1	Summary of Efficacy Variables: Intent-to-Treat-Infected Population
Listing 16.2.6.2	Influenza Symptoms: Intent-to-Treat Population
Listing 16.2.6.3	Temperature: Intent-to-Treat Population

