Listing 16.2.6.4	Subject-Rated Assessment of Daily Activities and Assessment of Appetite and Eating Patterns: Intent-to-Treat Population
Listing 16.2.6.5	Viral Titers and Viral Susceptibility: Intent-to-Treat Population
Listing 16.2.6.6	Symptom Relief Medications: Intent-to-Treat Population
Listing 16.2.6.7	Influenza-Related Complications: Intent-to-Treat Population
Listing 16.2.7.1	Adverse Events: Intent-to-Treat Population
Listing 16.2.7.2	Serious Adverse Events: Intent-to-Treat Population

Output Number	Output Title
Listing 16.2.8.1.1	Laboratory Tests - Hematology: Intent-to-Treat Population
Listing 16.2.8.1.2	Laboratory Tests - Chemistry: Intent-to-Treat Population
Listing 16.2.8.1.3	Laboratory Tests - Urinalysis: Intent-to-Treat Population
Listing 16.2.8.2	Blood and Urine Collection and Pregnancy Tests: Intent-to-Treat Population
Listing 16.2.8.3	Virology Specimen Collection and Influenza Antibodies Analysis: Intent-to-Treat Population
Listing 16.2.8.4	Vital Signs, Height, and Weight: Intent-to-Treat Population
Listing 16.2.8.5	Physical Examinations: Intent-to-Treat Population

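### Non-serious influenza-related complications in treated subjects without PCR confirmation reach no summary table, and no planned output states the antibiotic condition in the secondary objective

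*Protocol*

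**What the plan says.** **Reporting route.** Protocol section 11 (Adverse Events) states that "Influenza-related complications are not considered AEs unless they meet the criteria for SAEs". Protocol 10.2.4 has the investigator record sinusitis, otitis media, bronchitis and pneumonia, with the medications used to treat them, on the case report form instead.

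**Who is treated.** Protocol 8.1 admits subjects on a positive rapid antigen test or PCR test, or, where the sponsor has approved it, on symptoms: "During the period of approval, clinical symptoms alone will be adequate to meet Criteria 2".

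**Who is summarised.** SAP 5.2.1 lists IRC incidence as an effectiveness endpoint. SAP 4.2 limits ITTI to treated subjects with PCR-confirmed influenza and says "The ITTI population will be used for analyses of effectiveness". SAP section 9 plans one IRC table, 14.2.7: "Summary of Influenza-Related Complications and Hospitalizations: Intent-to-Treat Infected Population". The matching listing, 16.2.6.7, is "Influenza-Related Complications: Intent-to-Treat Population". Protocol 13.9 also places an IRC summary among the safety analyses, without naming a population. SAP 5.4 settles precedence: "In cases where the statistical analysis plan differs from the protocol, the statistical analysis plan will supersede the protocol".

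**What the objective asks.** Protocol 6.2 and SAP section 2 both frame the third secondary objective as the incidence of the four named complications, with an antibiotic condition and diagnosis after treatment has begun. The endpoint in SAP 5.2.1 is any complication as judged by the investigator, and SAP 5.2.2 counts these by preferred term.

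**The concern.** Two gaps follow.

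1. **Population.** New non-serious bronchitis, sinusitis, otitis media or pneumonia in a treated but unconfirmed subject enters no incidence figure. The adverse event tables exclude it by rule and the IRC table excludes it by population. A reader wanting the complication rate among everyone who received peramivir would have to count from a listing.
2. **Endpoint.** The planned count is broader than the objective. It includes complications that did not need antibiotics, so no output is specified to give the rate the objective names. The sentence is also open to two readings: the antibiotic condition may attach to all four diagnoses or only to pneumonia, the last in the list.

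The plan would then report a complication rate for confirmed subjects only, on a wider definition than its own objective. Protocol 13.9 adds doubt about whether a wider population was once intended, but this point does not allege an undeclared change.

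**Working it through.** **Tracing a non-serious IRC through the SAP outputs**

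| Subject | Adverse event tables (Safety) | Table 14.2.7 (ITTI) | Listing 16.2.6.7 (ITT) |
|---|---|---|---|
| Treated, PCR-confirmed | No | Yes | Yes |
| Treated, not confirmed | No | No | Yes |

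A serious IRC is an adverse event in either subject and reaches Table 14.3.1.5, "Treatment-Emergent Serious Adverse Events by System Organ Classification and Preferred Term: Safety Population". An antibiotic may appear in Table 14.3.7.1, "Concomitant Medications by Generic Name and Drug Classification: Safety Population", but by drug, with no stated link to a complication.

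**Tracing the antibiotic condition.** It is present in Protocol 6.2 and SAP section 2. It is absent from the endpoints (Protocol 7.1.2, SAP 5.2.1), the methods (Protocol 13.9, SAP 5.2.2) and the titles of Table 14.2.7 and Listing 16.2.6.7. The timing condition is largely met, because Protocol 10.1.1 makes a subject with an IRC at screening ineligible.

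**Size.** The plan has no figure to reproduce: there is no sample size calculation and no confirmation, IRC or antibiotic rate. The only document input is 120 subjects, all taken as treated. The assumptions below are for illustration.

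- Unconfirmed share: 5–30%. SAP 3.3.8 counts one positive RT-PCR on any study specimen as confirmation, and Protocol 10.3 provides up to four swab visits, so a low share is plausible.
- IRC rate: 5–10%.
- Share of IRCs needing antibiotics, if the condition covers all four diagnoses: 50–90%.
- If it covers pneumonia only: pneumonia is 10–30% of IRCs, with 80–100% needing antibiotics.

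*Population gap*

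- Subjects outside Table 14.2.7: 120 × 0.05 = 6 to 120 × 0.30 = 36.
- Expected IRCs among them: 6 × 0.05 = 0.3 to 36 × 0.10 = 3.6, fewer if some are serious.
- Chance of at least one, 1 − (1 − rate)^n: 1 − 0.95^6 = 0.26 to 1 − 0.90^36 = 0.98.

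*Endpoint gap, within ITTI*

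- ITTI size: 120 − 36 = 84 to 120 − 6 = 114.
- Expected IRCs: 84 × 0.05 = 4.2 to 114 × 0.10 = 11.4.
- Four-diagnosis reading, counted but outside the objective: 4.2 × (1 − 0.90) = 0.42 to 11.4 × (1 − 0.50) = 5.7. The upper end is 10% × 0.50 = 5 percentage points of a 10% rate.
- Pneumonia-only reading: 0 to 11.4 × 0.30 × (1 − 0.80) = 0.68. The upper end is 10% × 0.30 × 0.20 = 0.6 percentage points of a 10% rate.

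**The case against.** **ITTI is the natural population.** A complication of influenza presupposes influenza. Protocol 7.1.2 and 10.2 and SAP 5.2.1 treat IRC incidence as an effectiveness matter, and both documents assign effectiveness to ITTI. Protocol 13.9 is a mixed section that also covers disposition, so placement there does not prove a Safety-population intent, and the SAP prevails anyway. This stands as a defence of Table 14.2.7, which should stay. It does not supply a rate for all treated subjects.

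**Nothing is lost.** Every IRC is in the listing and serious ones are tabulated. On the assumptions above only a handful of events are at stake, and splitting them by age group leaves sparse cells. This is true and it limits the weight of the point. But only about 4 to 11 IRCs are expected in ITTI, so a few events more or fewer visibly move the reported rate.

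**Non-serious IRCs might count as treatment-emergent events.** SAP 3.3.8 defines these by events recorded on the case report form. However, that entry defines a class of adverse event, the SAP puts adverse events on their own form, and the protocol says non-serious IRCs are not adverse events. Nor does any rule turn an IRC into an adverse event after a negative PCR.

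**The antibiotic point is soft.** The protocol's own secondary endpoint is unqualified, the SAP follows it, and the unqualified count cannot understate the objective's rate. Counting by preferred term lets pneumonia be separated. Table shells are not in the documents, so an antibiotic row could exist. These points hold, and the claim is therefore limited to endpoints, methods and output titles. The mismatch between objective and endpoint begins in the protocol, and the SAP does not resolve it.

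**Conclusion.** The point holds. As written, the plan gives no incidence of non-serious IRCs that includes treated, unconfirmed subjects. It also specifies no output for the antibiotic-qualified rate its secondary objective names.

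The first statement and the missing wording rest on the text alone. The sizes rest wholly on assumed rates. The first gap could be negligible or a few events, and the size of the second depends mainly on which reading of the objective is meant.

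This is a reporting gap in a secondary objective. Protocol 7.1.1 does not name IRCs in the primary endpoint and Protocol 13.3 rules out formal hypothesis testing, so neither the primary analysis nor any decision rule is affected. It should still be corrected, because the plan otherwise reports a different quantity from the one it set out to estimate.

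**What to change.** In SAP 5.2.2 and section 9:

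- Keep Table 14.2.7 in ITTI.
- Add one Safety-population IRC summary, overall and by age group, beside the adverse event tables.
- In both tables show all post-dose IRCs by condition and, in separate rows by condition, those with an antibiotic recorded as treatment. Protocol 10.2.4 already captures these medications with each IRC.
- State to which of the four diagnoses the antibiotic condition applies, and that recorded treatment is a proxy for need.
- Record the added outputs in SAP section 6.

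As an editorial matter, make clear that the instruction in Protocol 10.2.4 not to report IRC signs and symptoms as adverse events is subject to the serious-event exception in Protocol section 11.

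The cost is SAP wording, one extra table and a set of antibiotic rows in each of two tables, with no new data collection. The drawbacks are that the antibiotic-treated rate rests on few events and depends on prescribing habits, and that the report must explain why IRCs appear in two populations.

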#### 11.1.1. Definitions

##### 11.1.1.1. Adverse Event

An AE is any untoward medical occurrence in a clinical study subject. No causal relationship with the study drug or with the clinical study itself is implied. An AE may be an unfavorable and unintended sign, symptom, syndrome, or illness that develops or worsens during the clinical study. Clinically relevant abnormal results of diagnostic procedures including abnormal laboratory findings (e.g., requiring unscheduled diagnostic procedures or treatment measures, or resulting in withdrawal from the study) are considered to be AEs.

Surgical procedures are not AEs but may constitute therapeutic measures for conditions that require surgery. The condition for which the surgery is required is an AE, if it occurs or is detected during the study period. Planned surgical measures permitted by the clinical study protocol and the condition(s) leading to these measures are not AEs, if the condition(s) was (were) known before the start of study treatment. In the latter case the condition should be reported as medical history.

Assessment of influenza symptoms will be documented and analyzed as a measure of effectiveness of the study treatment. These symptoms will not be reported as AEs unless the symptom(s) worsen to the extent that the outcome fulfills the definition of an SAE, which then must be recorded as such.

AEs are designated as “non-serious” or “serious.”

##### 11.1.1.2. Serious Adverse Event

An SAE is an adverse event that results in any of the following outcomes:

- Death
- Is life-threatening (subject is at immediate risk of death at the time of the event; it does not refer to an event that hypothetically might have caused death if it were more severe)
- Requires in-subject hospitalization (formal admission to a hospital for medical reasons) or prolongation of existing hospitalization

- Results in persistent or significant disability/incapacity (i.e., there is a substantial disruption of a person's ability to carry out normal life functions)
- Is a congenital anomaly/birth defect

Important medical events that may not result in death, are not life-threatening, or do not require hospitalization may be considered an SAE when, based upon appropriate medical judgment, they may jeopardize the subject or may require medical or surgical intervention to prevent one of the outcomes listed in this definition. Examples of such events include allergic bronchospasm requiring intensive treatment in an emergency room or at home, blood dyscrasias or convulsions that do not result in subject hospitalization, or the development of drug dependency or drug abuse.

Hospitalization, as per the institution's standard of care (SOC) to treat influenza in elderly patients is not considered an SAE and should not be reported as such. Any adverse event that causes a prolongation of an existing hospitalization must be reported as per [Section 11.1.5](#).

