## 8.2. Subject Exclusion Criteria

1. Subjects who in the opinion of the investigator require hospital admission to treat medical condition(s) which, in the Investigator's opinion, could represent complications of influenza. Note, hospitalization is not an exclusion criterion when it is the usual practice of the treating institution to hospitalize elderly patients with acute uncomplicated influenza.
2. Women who plan to breast-feed for the first 48 hours after study drug administration. However, women who suspend breast feeding for 48 hours after study administration may participate.
3. Employees of the study site, or immediate family members of study site employees
4. Presence of clinically significant signs of acute respiratory distress.
5. Clinical evidence of worsening of any chronic medical condition (temporally associated with the onset of symptoms of influenza) which, in the Investigator's opinion, indicates that such finding(s) could represent complications of influenza
6. Current clinical evidence, including clinical signs and/or symptoms consistent with a bacterial infection, including: otitis media, bronchitis, sinusitis and/or pneumonia, or active bacterial infection of any body site that requires therapy with oral or systemic antibiotics
7. Immunization against influenza with live attenuated virus vaccine (FluMist®) in the previous 14 days
8. History of alcohol abuse or drug addiction within 1 year prior to admission in the study
9. Participation in a study of any investigational drug or device within the last 30 days
10. Previous participation in study BCX1812-305 (pediatric study) or BCX1812-306 (this study)
11. Presence of any pre-existing illness that, in the opinion of the Investigator, would place the subject at an unreasonably increased risk through participation in this study or would make the subject unable to comply with the protocol.

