#### **11.1.2. Method, Frequency, and Time Period for Detecting Adverse Events and Reporting Serious Adverse Events**

Reports of AEs are to be collected from the time the subject signs the informed consent through the follow-up period ending on Day 14. The Investigator or designee must completely and promptly record each AE. The Investigator should attempt, if possible, to establish a diagnosis based on the presenting signs and symptoms. In such cases, the diagnosis should be documented as the AE and not the individual sign/symptom. If a clear diagnosis cannot be established, each sign and symptom must be recorded individually. If a final diagnosis is established during evaluation or treatment, the source documents will be updated accordingly.

The Investigator should attempt to follow all unresolved AEs and/or SAEs observed during the study until they are resolved, or are judged medically stable, or are otherwise medically explained.

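### The SAE exemption for standard-of-care influenza hospitalization in the elderly is not limited to the enrolment stay or to uncomplicated influenza, so some post-dose admissions for worsening influenza can go unreported at 65 or over but count as SAEs under 65

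*Protocol*

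**What the plan says.** Protocol 11.1.1.2 lists hospitalization among the outcomes that make an adverse event serious: "Requires in-subject hospitalization (formal admission to a hospital for medical reasons) or prolongation of existing hospitalization". At the end of the section it makes an exception: hospitalization under the institution's standard of care "to treat influenza in elderly patients is not considered an SAE and should not be reported as such". The next sentence gives the only qualification placed beside the exception: "Any adverse event that causes a prolongation of an existing hospitalization must be reported as per" section 11.1.5.

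Two other rules depend on the SAE definition. Section 11.1.1.1 says of influenza symptoms: "These symptoms will not be reported as AEs unless the symptom(s) worsen to the extent that the outcome fulfills the definition of an SAE". The Adverse Events text at the start of protocol section 11 says: "Influenza-related complications are not considered AEs unless they meet the criteria for SAEs".

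The exception appears to mirror exclusion criterion 1 (protocol 8.2), where a hospital stay does not bar entry when "it is the usual practice of the treating institution to hospitalize elderly patients with acute uncomplicated influenza".

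On timing, section 11.1.2 says: "Reports of AEs are to be collected from the time the subject signs the informed consent through the follow-up period ending on Day 14". Section 10.2.5 asks for additional information on any admission during the study. SAP 3.3.2 presents all analyses by age group, and SAP 5.3.1 plans a separate summary of treatment-emergent SAEs.

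**The concern.** The exception has a legitimate purpose. If a hospital routinely admits older patients with uncomplicated influenza, that stay is not an untoward event and would only add noise to the SAE tables. The wording, however, reaches further than that purpose. It is tied neither to the admission that accompanies enrolment nor to uncomplicated illness, so it can be read to cover an admission several days after dosing because the influenza got worse.

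Safety is the primary objective and the primary endpoint (protocol 6.1 and 7.1.1), and at least 80 of about 120 subjects will be 65 or over. An event lost here leaves the SAE and TEAE tables and the 24-hour report under 11.1.5. Whether it is lost depends on the admission habits of the site, not on what happened to the subject. The exception applies to one age group only, so the planned SAE displays by age would apply different definitions to the groups shown side by side, with fewer countable events among the elderly. There is no control arm against which an under-count could be noticed.

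**Working it through.** The documents state no admission rate, power or computed sample size, so there is no figure of the plan to reproduce. The check is first one of logic, then an illustration.

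**Same event, two ages.** Take a subject dosed as an outpatient and admitted on Day 3 because influenza symptoms worsened. No other seriousness criterion is met, and the site regards the stay as its standard of care.

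| Step | Under 65 | 65 or over |
|---|---|---|
| Hospitalization criterion (11.1.1.2) | Met | Met, then removed by the exception |
| Other seriousness criteria | Not met | Not met |
| SAE? | Yes | No, with an instruction not to report it as one |
| AE under the symptom rule (11.1.1.1)? | Yes, because it is an SAE | No, because it is not an SAE |
| Prolongation clause (11.1.1.2) | Not needed | Does not help: there was no existing stay to prolong |

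**Comparison with exclusion criterion 1.** Both texts rest on what the institution usually does. Criterion 1 specifies acute uncomplicated influenza; 11.1.1.2 says only influenza. Criterion 1 states no timing rule, but as an eligibility criterion it is applied before dosing. Section 11.1.1.2 sits inside a reporting period that runs from consent to Day 14, and nothing confines it to part of that period.

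**Illustration of size.** Inputs:
- n = 80, the minimum number of elderly subjects (protocol 10.1; SAP 1.1), with 120 - 80 = 40 left under 65.
- r, the proportion admitted after dosing for worsening influenza with hospitalization as the only seriousness criterion. Assumed; not in the documents.
- f, the share of those elderly admissions that sites class as standard of care. Assumed; not in the documents.

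Expected reported elderly events = n × r × (1 - f).

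| r | f = 0 | f = 50% | f = 100% | Expected under 65 (40 × r) |
|---|---|---|---|---|
| 2% | 1.6 | 0.8 | 0 | 0.8 |
| 5% | 4.0 | 2.0 | 0 | 2.0 |
| 10% | 8.0 | 4.0 | 0 | 4.0 |

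With 4 actual admissions among 80, the exact (Clopper-Pearson) 95% limits for what would be reported are:
- none exempted: 4/80 = 5.0% (1.4-12.3%)
- half exempted: 2/80 = 2.5% (0.3-8.7%)
- all exempted: 0/80, upper limit 1 - 0.025^(1/80) = 4.5%

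In the last case the interval shown for the elderly would exclude the true 5.0%. At r = 5% in both age groups and f = 50%, the display would show 2.5% in the elderly against 5% under 65, although the underlying rates are equal.

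**The case against.** The strongest reply is that the scenario strains the words. A hospital that routinely admits older patients with influenza would do so at presentation. Someone sent home on Day 1 and admitted on Day 3 was admitted because of deterioration, not routine, so the ordinary hospitalization criterion applies and the event is an SAE. An investigator may well read it so, and this was probably the intent. But the protocol gives no criterion that separates a routine admission from one for worsening, and it pairs the exception with an instruction not to report. Two sites can therefore classify identical events differently.

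Other points limit the concern and stand:
- A reader might infer that serious deterioration in the elderly escapes reporting altogether. It does not. Death, life-threatening events, lasting disability and important medical events remain SAEs at every age. Admissions for conditions other than influenza are untouched.
- A reader might infer that 11.1.1.2 discards an explicit pre-dosing condition found in criterion 1. Criterion 1 has no such condition; its timing follows only from its being an eligibility rule. The one stated limit that is missing is the word *uncomplicated*.
- A reader might infer that the admission disappears from the database. Section 10.2.5 still collects information on it. Collection does not make it an SAE, though, and the SAP's hospitalization summary (5.2.2) counts only stays due to a TEAE, so it does not bring a non-AE admission back.
- An age-specific exception follows from age-specific eligibility, and the study tests no hypothesis. That justifies having an exception, but not its open-ended scope: descriptive tables also need one definition across the groups displayed.

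**Conclusion.** The concern holds as a gap in definition. Read together, 11.1.1.2 and 11.1.1.1 allow a new post-dose admission of a subject aged 65 or over for worsening influenza to be recorded as neither SAE nor AE, while the same admission under 65 is an SAE. Two conditions must both be met: hospitalization is the only seriousness criterion, and the site treats the stay as standard of care.

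The size cannot be established. The documents give neither an admission rate nor the number of sites that routinely admit older patients. The range from 4/80 to 0/80 rests on an assumed 4 admissions, and 0/80 is the extreme case in which every one is exempted. It should not be read as the expected result, and the documents do not show that the elderly SAE rate will in fact be understated. The gap itself does not depend on any assumed rate. It does not invalidate the trial, but it should be closed, because it lies in a key definition behind the primary endpoint and is cheap to correct.

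**What to change.** Reconcile 11.1.1.2 with exclusion criterion 1:

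- Limit the exception to a routine stay for acute uncomplicated influenza that began, or was decided under the institution's usual practice, at the enrolment encounter.
- State that a later admission, or a prolongation, because influenza worsened or became complicated, or because of any other adverse event, is an SAE at every age.
- Keep planned procedures outside, as 11.1.1.1 already does.

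Tying the exception to the enrolment encounter, not to the moment of dosing, matters. A rule that makes every admission decided after dosing an SAE would sweep in planned surgery, and also routine same-day admissions, since dosing follows eligibility as soon as possible.

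Add one yes/no CRF item: was this stay a routine admission decided at enrolment?

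The cost is a protocol wording change and one CRF field. The downside is that a few additional admissions will be reported as SAEs; the CRF item lets the analysis identify them.
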